6.4.4.1.1. Missing data handling and total score calculation

The overall and domain scores of the AQLQ +12 are derived as the average of the corresponding items; the analysis will be based on the available data.

For incomplete data, the overall AQLQ +12 score for a particular visit will not be calculated if 3 or more responses are missing with no more than 1 per domain. For the symptom and activity domain total scores, calculation will require no more than 1 missing item. Total scores for the other 2 domains will be regarded as missing if 1 or more item is missing.

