6.4.4. AQLQ +12

6.4.4.1. Variable Definition

The AQLQ +12 is a modified version of the standardized AQLQ which measures functional impairments experienced by adults ≥ 17 years of age. The AQLQ +12 is valid for patients aged 12-70 years.

The AQLQ +12 is a 32-item instrument administered as a self assessment at weeks 4, 8, 12, 16, 20, and 24. Patients are asked to recall their experiences during the previous 2 weeks and to score each question on a 7-point scale (7 = no impairment, 1 = severe impairment).

The 32 questions (items) in the AQLQ +12 are divided into 4 domains:

- Activity limitations: Items 1-5, 11, 19, 25, 28, 31, 32

- Symptoms: Items 6, 8, 10, 12, 14, 16, 18, 20, 22, 24, 29, 30
- Emotional function: Items 7, 13, 15, 21, 27
- Environmental stimuli: Items 9, 17, 23, 26

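### The AQLQ +12 overall-score rule attaches a condition for keeping a form to the rule for discarding it, so read literally it scores many of the least complete forms

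*SAP*

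**What the plan says.** SAP section 6.4.4.1 defines the instrument: "The 32 questions (items) in the AQLQ +12 are divided into 4 domains". Each domain's items are then listed.

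Section 6.4.4.1.1 says the overall and domain scores are "derived as the average of the corresponding items; the analysis will be based on the available data". For incomplete forms it gives three rules:

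- **Overall score:** it "will not be calculated if 3 or more responses are missing with no more than 1 per domain".
- **Symptom and activity domains:** "For the symptom and activity domain total scores, calculation will require no more than 1 missing item".
- **Emotional and environmental domains:** a single blank item makes the domain score missing.

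Nothing elsewhere replaces the overall-score rule. Protocol section 6.4 describes the questionnaire without a missing-item rule. The change tables in SAP section 10 do not touch this sentence. SAP section 4.4 plans no imputation for variables of this kind.

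**The concern.** Grammatically, the sentence is one discard condition with two parts that must both hold: at least 3 blanks, and no domain with more than 1. The first part points the sensible way. The second is what one would ask of a form worth keeping. Joined to a discard rule, it protects a form from rejection as soon as two blanks fall in the same domain.

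The sentence is the only completeness check on the overall score, because a score that is kept is the mean of whatever items were answered. Under SAP section 6.4.4.2 that score enters the MMRM of change from baseline, the summary and CMH test of patients improving by at least 0.5, and the subgroup forest plots. Programmed as written, nearly complete forms would be dropped and forms lacking a whole domain would be averaged over the remaining domains. A programmer who sees the problem would have to choose another rule without guidance.

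**Working it through.** **Inputs (SAP section 6.4.4.1)**

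- "Activity limitations: Items 1-5, 11, 19, 25, 28, 31, 32": 11 items
- "Symptoms: Items 6, 8, 10, 12, 14, 16, 18, 20, 22, 24, 29, 30": 12 items
- "Emotional function: Items 7, 13, 15, 21, 27": 5 items
- "Environmental stimuli: Items 9, 17, 23, 26": 4 items

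The plan's own figure reproduces: 11 + 12 + 5 + 4 = 32, and each of items 1 to 32 is listed exactly once.

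**Literal rule.** Discard if (total blanks ≥ 3) and (largest number of blanks in any domain ≤ 1).

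**Three blanks.** A discarded pattern has one blank in each of three different domains:

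- 11×12×5 + 11×12×4 + 11×5×4 + 12×5×4 = 660 + 528 + 220 + 240 = 1648
- possible patterns: C(32,3) = 4960
- discarded: 1648/4960 = 33.2%

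**Four blanks.** A discarded pattern has one blank in every domain:

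- 11×12×5×4 = 2640
- possible patterns: C(32,4) = 35960
- discarded: 2640/35960 = 7.3%

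**Five or more blanks.** With four domains, at least one must hold two or more blanks, so the second part of the condition fails. Discarded: 0.

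**Individual patterns** (blanks in activity/symptoms/emotional/environmental):

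| Pattern | Blanks | Literal result |
|---|---|---|
| 1/1/1/0 | 3 | not scored |
| 1/1/1/1 | 4 | not scored |
| 3/0/0/0 | 3 | scored |
| 2/1/0/0 | 3 | scored |
| 0/0/0/4 (environmental wholly blank) | 4 | scored |
| 0/0/5/0 (emotional wholly blank) | 5 | scored |
| 2/2/1/1 | 6 | scored, with all four domain scores missing |
| 11/0/0/0 (activity wholly blank) | 11 | scored |
| 0/12/0/0 (symptoms wholly blank) | 12 | scored from 20 items |
| 11/12/5/3 | 31 | scored from 1 item |

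**Possible repairs.** The sentence could be mended in at least three ways. Shares of patterns discarded:

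| Rule | 2 blanks | 3 blanks | 4 blanks | 5 or more |
|---|---|---|---|---|
| As written | 0% | 33.2% | 7.3% | 0% |
| A: discard if ≥3 blanks, or >1 in any domain | 27.6% | 100% | 100% | 100% |
| B: keep only if ≤3 blanks and ≤1 per domain | 27.6% | 66.8% | 100% | 100% |
| C: drop the per-domain clause | 0% | 100% | 100% | 100% |

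The 27.6% is [C(11,2) + C(12,2) + C(5,2) + C(4,2)] / C(32,2) = (55 + 66 + 10 + 6)/496 = 137/496. The 66.8% is (4960 − 1648)/4960. The repairs agree from four blanks upward and differ at two and three.

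**The case against.** The strongest reply is that this is a garbled sentence, not a perverse rule. Its first half is sensible, the trailing clause looks like a leftover statement of what is tolerated, and no one would mean to score a form with 31 of 32 items blank. That is probably how the sentence arose. It follows that only the per-domain clause is misplaced; a reader might infer that the whole rule runs backwards, and it does not. The slip still matters, because the text does not say which sensible rule was meant and the candidates differ.

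A reader might also infer that the sentence contradicts the domain rules that follow it. It does not. Those rules govern domain scores and this one governs the overall score, and a plan may set different tolerances for each. The SGRQ rule in SAP section 6.4.6.1.1 does so: the symptoms domain tolerates 2 missing of 8 responses and the total tolerates 12 of 50, so a total is possible with all 8 symptom responses blank. What stands is that the literal AQLQ +12 rule is out of line with the strict domain rules beside it. Unlike the SGRQ rule, it also sets no upper limit on blanks.

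It is fair, too, that the percentages show no effect on any estimate, and that the endpoint ranks low: AQLQ +12 is listed among the other efficacy endpoints (SAP sections 2.2.3 and 6.4.1), is analysed only in patients aged 12 to 70 (section 3.1.1), and plays no part in the primary endpoint's definition of lost asthma control (section 6.2.1).

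**Conclusion.** The rule is wrong as written, and the defect is small. On the literal reading, the forms discarded are exactly those with 3 or 4 blanks all in different domains. The forms wrongly kept are not only those with 5 or more blanks: about two thirds of three-blank patterns and 92.7% of four-blank patterns (33320/35960) are also scored, including a wholly blank environmental domain.

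Two assumptions carry this: that both clauses are programmed as a single joint condition, and, if the percentages are to be read as probabilities, that blanks fall at random over the 32 items. They should not be read as expected losses of patients; without a rate of incomplete forms, the number affected cannot be calculated.

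A reader might infer a threat to the trial's main conclusions. The documents do not support that: the fixed testing sequence (SAP sections 4.3 and 6.3.1) does not include AQLQ +12. What is exposed is the reproducibility and quality of the AQLQ +12 results themselves.

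**What to change.** Replace the sentence before unblinding with a rule in the intended direction. One suitable wording: *Set the overall AQLQ +12 score to missing at a visit when three or more of the 32 items are blank, or when any single domain has more than one blank item.* This is repair A above.

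The sponsor should confirm the exact threshold against the instrument's scoring instructions, which are not in these documents, because repairs B and C also fit the sentence. Any of the three would reject every form with four or more blanks.

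The cost is one SAP sentence and the matching line of programming, with no change to data collection. The downside of the suggested wording is that it also drops two-blank forms with both blanks in one domain, which the current sentence keeps. If the scoring instructions allow such forms, the per-domain limit should be relaxed to match.

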6.4.4.2. Analysis

Summary statistics of actual values and change from baseline to each scheduled visit will be provided by treatment group.

Analysis of the change from baseline to each scheduled visit will use the same MMRM model described in Section 6.4.3.2 with the exception of inclusion of sex and height in the model. A line graph will be provided for the LS mean change from baseline over time (at each visit).

AQLQ +12 at Week 24 will additionally be examined for the selected subgroups defined in Section 3.4. The analysis of subgroups will use a MMRM model similar to the one described above. Subgroups will be presented graphically using forest plots.

The proportion of patients achieving an increase of ≥ 0.5 in the AQLQ +12 score from baseline to each scheduled visit will be summarized. A stratified (based on randomization strata) Cochran-Mantel-Haenszel (CMH) test will be used to analyze the proportion of patients achieving an increase of ≥ 0.5 in the AQLQ +12 score from baseline to Week 24.

6.4.5. ACQ-6

6.4.5.1. Variable Definition

The ACQ-6 was developed to measure asthma control. The ACQ-6 is a 6-item instrument; each item is scored on a scale of 0 to 6 (higher scores are an indication of poorer asthma control). At weeks 4, 8, 12, 16, 20, 24, and 32 (follow-up), the patient answers each of the 6 questions, identifying the response that best describes how the patient has been during the past week.

6.4.5.1.1. Missing data handling and total score calculation

The overall score of the ACQ-6 is derived as the average of the individual item scores; the analysis will be based on the available data.

For incomplete data, the following rules will apply:

1. Total score for the visit will not be calculated if Question 1 is left blank, irrespective of the completion of the remaining questions.

2. A missing score on post screening questionnaire for Questions 2-6 will be imputed based on the total scores from the previous visit, as long as at least 3 out of the 5 questions have responses for the current visit (ie, at least half of the remaining questions are answered).

The formula is: (total sum of non-missing scores for the current visit / total sum of scores for the previous visit for questions answered for the current visit) * (score for the missing question on the previous visit)

3. Total score at screening will not be calculated if Question 1 or two or more among Questions 2-6 is left blank. A missing score for Questions 2-6 at screening will be replaced by an average of the available scores.

6.4.5.2. Analysis

Summary statistics of actual values and change from baseline to each scheduled visit will be provided by treatment group.

Analysis of the change from baseline to each scheduled visit will use the same MMRM model described in Section 6.4.3.2 with the exception of inclusion of sex and height in the model.

[REDACTED] A line graph will be provided for the LS mean change from baseline over time (at each visit).

ACQ-6 at Week 24 will additionally be examined for the selected subgroups defined in Section 3.4. The analysis of subgroups will use a MMRM model similar to the one described above. Subgroups will be presented graphically using forest plots.

The proportion of patients achieving a reduction of ≥ 0.5 in the ACQ-6 score from baseline to each scheduled visit will be summarized. A stratified (based on randomization strata) CMH test will be used to analyze the proportion of patients achieving a reduction of ≥ 0.5 in the ACQ-6 score from baseline to Week 24.

6.4.6. SGRQ

6.4.6.1. Variable Definition

St. George's Respiratory Questionnaire (SGRQ) is a health status survey specific for chronic obstructive pulmonary disease and other respiratory diseases. The SGRQ consists of 2 parts: Part 1 produces a symptom score and Part 2 produces an activity and impacts score. A total score is also calculated. The SGRQ is administered as a self assessment at weeks 12 and 24.

The questions in the SGRQ are divided into 3 domains:

- Symptoms: Questions 1-8
- Activity: Questions 11, 15
- Impacts: Questions 9-10, 12-14, 16-17

The SGRQ requests a single response to each of Questions 1-10 and 17; whereas Questions 11-16 each request multiple responses, resulting in a total of 50 responses across the questionnaire.

6.4.6.1.1. Missing data handling and total score calculation

Each questionnaire response has a unique empirically derived ‘weight’ (the lowest possible weight is 0 and the highest is 100). The weights associated with each response is provided in [Appendix C](#). Derivation of each domain and total score is as follows:

1. The weights for all items with a positive response are summed.
2. The weights for missing items are deducted from the maximum possible weight for each domain (or total) score. The maximum possible weights for each domain and total score are 662.5 (symptoms), 1209.1 (activity), 2117.8 (impacts), and 3989.4 (total).
3. The score is calculated by dividing the summed weights (from Step 1) by the adjusted maximum possible weight for the domain or total score (from Step 2) and expressing the result as a percentage:

$$\text{Score} = 100 \times (\text{Sum of weights from positive items in the domain (or total)} / \text{Sum of weights for all items in the domain (or total)})$$

Thus, scores are expressed as a percentage of overall impairment, where 100 represents the worst possible health status and 0 represents the best possible health status. The questionnaire requests a single response to each of Questions 1-10 and 17. If multiple responses are given to any one of these questions, then the weights for the positive responses for that question will be averaged.

A score will only be calculated if at least 75% of the responses for the total and/or domain score are non-missing for a given visit. If more than 25% of the questions are missing, then the total and/or domain score will be considered missing for that visit. For the symptoms domain (8 total responses), this threshold translates to a maximum of 2 missed responses that can be tolerated. For the activity domain (16 total responses), a maximum of 4 missed responses can be tolerated. For the impacts domain (26 total responses), a maximum of 6 missed responses can be tolerated. For the total score (50 total responses), a maximum of 12 missed responses can be tolerated.

6.4.6.2. Analysis

Summary statistics of actual values and change from baseline to each scheduled visit will be provided by treatment group.

Analysis of the change from baseline to each scheduled visit will use the same MMRM model described in Section [6.4.3.2](#) with the exception of inclusion of sex and height in the model.

The proportion of patients achieving a reduction of ≥ 4 in the SGRQ score from baseline to each scheduled visit will be summarized. A stratified (based on randomization strata) CMH test will be used to analyze the proportion of patients achieving a reduction of ≥ 4 in the SGRQ score from baseline to Week 24.

6.4.7. EQ-5D

6.4.7.1. Variable Definition

The EQ-5D consists of the descriptive system and the visual analogue scale (VAS). The descriptive system is comprised of 5 health domains (mobility, self care, usual activities, pain/discomfort, anxiety/depression) and each domain has 3 levels of response (1=no problems, 2=some problems, 3=major problems). For the VAS component, the response is indicated on the

visual analogue scale provided and the value corresponding to the scale is recorded in the designated box (0=worst imaginable health state, 100=best imaginable health state). The EQ-5D is administered as a self assessment at week 24.

6.4.7.1.1. Missing data handling and total score calculation

[figure not shown]
For the descriptive system, there should be only one response recorded for each domain. If multiple responses are indicated for a single domain, the response will be treated as missing.

A unique health state is defined by a 5-digit code, combining levels across each of the 5 domains. For example, 11111 would indicate no problem in any domain and 33333 would indicate major problems in all domains.

6.4.7.2. Analysis

For the descriptive system, the number and percentage of patients at each of the levels 1-3 will be summarized descriptively for each domain.

For the VAS component, summary statistics of actual values and change from baseline to Week 24 will be provided by treatment group. Analysis of the change from baseline to Week 24 will be performed using an analysis of covariance (ANCOVA) model with fixed effects for treatment, age group, OCS dose at baseline, and baseline value as covariate.

6.4.9. Asthma Control Diary

6.4.9.1. Variable Definition

6.4.9.1.1. Asthma symptom scores

The asthma symptom score will be determined every morning and evening by the patient and recorded in the daily asthma control diary. The asthma symptom score is used to measure how much patients are bothered by their asthma symptoms. Asthma symptom score will be rated on a scale, with higher scores indicating more severe symptoms. The daytime asthma symptom score (range: 0-5) will be assessed in the evening and indicate how the patient felt earlier that same day. The nighttime asthma symptom score (range: 0-4) will be assessed in the morning and indicate how the patient felt during the previous night. Total asthma symptom score (range: 0-9) will be derived as the sum of the daytime and nighttime symptom scores.

6.4.9.1.2. Total reliever use

The number of times SABA reliever therapy is used will be recorded by the patient, once in the morning and once in the evening. Total reliever use will be derived as the sum of the morning and evening counts.

6.4.9.1.3. Nighttime awakenings

Nighttime awakenings will be recorded daily in the morning to indicate whether the patient was awakened during the previous night due to asthma. An awakening-free night (y/n) is defined as a night during which the patient did not experience a nighttime awakening.

6.4.9.1.4. Peak expiratory flow

Peak expiratory flow (PEF) is the maximum speed of exhalation, measured by a PEF meter. Morning (AM) and evening (PM) ambulatory PEF will be measured daily by the patient and the maximum of 3 separate readings will be recorded in the asthma control diary.

6.4.9.2. Analysis

Compliance with the daily diary assessments will be derived for each patient as an additional measure of protocol adherence. A diary compliant day will be defined as a day with non-missing values for all diary assessments, including AM/PM asthma symptom score, AM/PM reliever use, AM/PM PEF, and nighttime awakenings. Diary compliance will be derived as a percentage over the treatment period:

- $\text{Diary compliance (\%)} = 100 \times (\text{total number of diary compliant days} / \text{total number of days during the treatment period})$

The treatment period for diary compliance extends from the first day of study drug to the last day of study drug. Note that, in this analysis, missing data will be treated as non-compliant (eg, if compliance cannot be assessed for a given day due to missing data, then the day will not be counted as a diary compliant day).

PEF measurements collected in the morning and in the evening will be summarized separately. Asthma symptoms collected in the morning and in the evening will be summed to derive a total

daily symptom score. Total reliever use will be derived as the sum of the morning and evening counts.

A weekly average of the daily diary measures (AM/PM PEF, total asthma symptom score, and total reliever use) will be derived (see [Table 6](#) for the definition of analysis days for diary data). The average will be calculated as the sum of all values divided by the number of non-missing assessments. There will be no imputation of missing data. At least 4 of the 7 measurements need to be recorded for a week to be included in the analysis; otherwise the week will be treated as missing.

Nighttime awakenings will be derived and analyzed as a percentage over the treatment period, derived as:

$$\text{Awakening-free nights (\%)} = 100 \times (\text{total number of awakening-free nights} / \text{total number of days during the treatment period})$$

The treatment period is defined in [Section 6.4](#). Note that missing data will be treated as non-responders in this analysis (eg, if response for nighttime awakenings is missing for a given day, then the day will not be counted as an awakening-free night).

Summary statistics of actual values and change from baseline to each week will be provided by treatment group.

Analysis of the change from baseline to each week will use a similar MMRM model as described in [Section 6.4.3.2](#) with the exception of inclusion of sex and height in the model.

Analysis of the percentage of awakening-free nights will be performed using an analysis of variance (ANOVA) model with fixed effects for treatment, age group, and OCS dose at baseline.

A line graph presenting the LS mean change from baseline over time (at each week) will be provided for morning PEF, evening PEF, total asthma symptom score, and total reliever use by treatment group.

